### Sentinel node in cervical cancer Version 1.2 180914 11. STATISTICAL CONSIDERATIONS

This study is designed to evaluate the application of the sentinel node (SLN) technique in determining the pelvic lymph node (LN) status in patients with early stage cervical cancer ( stage 1a2 to 2a1) planned for primary surgery with either a radical hysterectomy or radical abdominal trachelectomy.

The main statistical endpoint will be sensitivity and false negative rates /negative predictive value calculated per patient. The sensitivity is the proportion of patients who test as SLN (+) among the patients who have LN metastases (LN+). The patients will, according to the Swedish national guidelines for early stage cancer undergo a full pelvic lymphadenectomy, however with separate removal of SLN as defined above, hence serve as their own controls. As lymph node status (lymph node metastases or no lymph node metastases) is a definite parameter (false positive result can by definition not occur) specificity and positive predictive values will not be reported in this study.

The time for accrual may have to be revised revised after inclusion of additional participating centers.

We used the Fleming two stage design for evaluation of study termination for evaluating if the technique is not working well, as expected or better (Fleming, 1982).

The null hypothesis that the sensitivity is 85% will be tested against one-sided alternative. The study is terminated after stage one if it is unlikely that the sensitivity is  $\geq$  95% or if sensitivity is significantly higher than 85%. In the first stage, 34 LN+ patients will be accrued. If there are 30 or fewer responses in these 34 patients, the study will be stopped for futility. If there are at least 33 responses in 33 patients, the study will be stopped and the null hypothesis rejected. Otherwise, 28 additional patients will be accrued for a total of 62 node positive patients. The null hypothesis will be rejected if 58 or more responses are observed in 62 patients. This design yields a type I error rate of 0.05 and power of 0.8 when the true sensitivity is 92.5

For the first stage we estimated a total of 226 patients to be included taking into consideration a 95% bilateral SLN detection rate, and an estimated 15% rate of node positivity including an increase in node positivity rates due to ultrasectioning and immunohistochemistry. For the second stage, another 187 patients have to be included. As the number of node positive patients will be reported continuously to the study coordinator this will be decisive of the number of patients that has to be included for each stage.

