#### 9.0 DURATION OF STUDY

The study includes a radical hysterectomy/ radical abdominal trachelectomy with detection of SLN followed by a full pelvic lymphadenectomy along both the UPP and LPP.

The patient may withdraw from the protocol at any time prior to surgery or at any time until retrieval of postoperative data until one year after surgery.

The study is initiated at Lund University hospital with a planned later inclusion of the second investigating center which may motivate a revision of the study protocol related estimated time for enrollment of patients and for accreditation of the second centre and surgeons.

Assuming that the prevalence of pelvic lymph node metastases is 15 % 227 patients will be needed to obtain 34 lymph node positive observations. Given a 95% bilateral detection rate of SLN's approximately 15 patients more will need to be included. On the other hand, ultrasectioning and IHC of SLN's is estimated to increase the proportion of patients with nodal metastases by identifying micro metastases. As there will be a continuous report of node positive patients to the study coordinator an interim analysis will start after 36 node positive patients regardless of the total number of patients included. (see 11, statistical considerations) Accrual will not be suspended during the interim analysis as the intervention is estimated to pose minimal risk to patients and the national treatment protocol, recommending a full lymphadenectomy, will be followed, even in the event of futility.

If the trial continues to stage 2, another 28 node positive patients (total 187 patients) will be required. (see 11, statistical considerations)

Given an estimate that the accrual rate is 2,5 cervical cancer patients per month per center, a total of 45 months will be required to reach 226 cervical cancer patients and a total of an additional 37 months to reach 413 patients.

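### The stage-1 success stop is printed as 33 of 33 in a 34-patient stage, and the interim trigger of 36 node-positive patients has no bounds written for it

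*Combined protocol and SAP*

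**What the plan says.** Section 11 describes a Fleming two-stage design testing a null sensitivity of 85% against a one-sided alternative.

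- Stage-1 size: "In the first stage, 34 LN+ patients will be accrued".
- Futility: "If there are 30 or fewer responses in these 34 patients, the study will be stopped for futility".
- Success: "If there are at least 33 responses in 33 patients, the study will be stopped and the null hypothesis rejected".
- Continuation: "Otherwise, 28 additional patients will be accrued for a total of 62 node positive patients". The null is then rejected at 58 or more of 62.
- Operating characteristics: "This design yields a type I error rate of 0.05 and power of 0.8 when the true sensitivity is 92.5".

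The Overview study plan and section 9 place the interim analysis after 36 node-positive patients and refer the reader to section 11. The number 36 does not appear there. Section 9 adds that accrual continues during the interim analysis.

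On enrolment, section 9 says, at 15% prevalence, "227 patients will be needed to obtain 34 lymph node positive observations". It continues: "Given a 95% bilateral detection rate of SLN's approximately 15 patients more will need to be included". It then notes that ultrasectioning and immunohistochemistry should raise the share of node-positive patients. Section 11 says instead: "For the first stage we estimated a total of 226 patients to be included taking into consideration a 95% bilateral SLN detection rate", and counts the ultrasectioning gain within its 15%.

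**The concern.** The two stage-1 bounds belong to one look at the data but use different denominators. A threshold of at least 33 out of 33 can only mean all 33, which is an odd way to state a bound in a stage of 34. Read literally, 33 of 34 with the single miss among the first 33 goes on to a second stage of 28 more LN+ patients. A bound of 33 of 34 would stop there and reject.

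The trigger raises a different problem. If the interim is run on 36 patients, section 11 gives no thresholds for that number, and the readings a team might improvise differ widely in error control. Because accrual is not suspended, LN+ patients beyond the 34th will probably exist when the decision is taken, and nothing says whether they count. This is the stop-or-continue rule on the main endpoint.

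**Working it through.** **Inputs (section 11).** p0 = 0.85; n1 = 34; futility at 30 or fewer; n2 = 28; final rejection at 58 or more of 62. True sensitivities examined: 0.925 (where power is stated) and 0.95 (named in the futility wording). X1 and X2 are the binomial counts in the two stages.

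**1. Reproducing the stated type I error.** With success at 33 or more of 34, only 31 and 32 continue:

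P(reject) = P(X1 ≥ 33) + P(X1 = 31)·P(X2 ≥ 27) + P(X1 = 32)·P(X2 ≥ 26)

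At 0.85: 0.0279 + 0.1310 × 0.0627 + 0.0696 × 0.1871 = 0.0279 + 0.0082 + 0.0130 = **0.0491**, which rounds to the stated 0.05.

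**2. The printed rule, read literally** (reject if the first 33 all respond; otherwise futility at 30 or fewer of 34, else continue). It parts from step 1 only at 33 of 34 with the miss among the first 33, which has probability 33·p³³·(1−p). On that path at least 25 of 28 are then needed. So:

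P(reject, printed) = P(reject, step 1) − 33·p³³·(1−p)·P(X2 < 25)

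At 0.85: 0.0491 − 0.0232 × (1 − 0.3772) = **0.0347**.

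| True sensitivity | P(reject), ≥33/34 | P(reject), printed | P(rules part) | P(then fails 25/28) |
|---|---|---|---|---|
| 0.85 | 0.049 | 0.035 | 0.023 | 0.623 |
| 0.925 | 0.517 | 0.488 | 0.189 | 0.155 |
| 0.95 | 0.805 | 0.790 | 0.304 | 0.049 |

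Other readings of the success stop, with the remaining bounds unchanged, also miss 0.05: 34 of 34 gives 0.034, no success stop gives 0.033, and a stage of 33 followed by 29 gives 0.027.

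**3. Carrying the bounds to 36.** With 26 further patients and a final bound of 58 of 62, at 0.85:

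- Counts unchanged (30 or fewer stop, 33 or more reject): 0.1906 + 0.0024 = **0.193**.
- Allowed misses unchanged (32 or fewer stop, 35 or more reject): 0.0212 + 0.0222 = **0.043**.

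If 28 patients were added after 36, the total would be 64, not 62.

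**4. Where 36 may come from.** 34/0.95 = 35.8. Also 227 + 15 = 242, and 242 × 0.15 = 36.3. Both match 36.

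**5. The enrolment figures.** 34/0.15 = 226.7, so 226 or 227 carries no detection allowance. 226 × 0.15 = 33.9, and 33.9 × 0.95 = 32.2. With the allowance, 34/(0.15 × 0.95) = 238.6. The second stage is the same: 28/0.15 = 186.7, the plan's 187, again with no allowance.

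**The case against.** The best counter-argument is that a competent reader would repair the text unaided. The wording at least 33 makes no sense if 33 is the maximum, the neighbouring sentences fix the stage at 34, and section 10 has the study statistician among those who review the interim data. No section mentions a first 33 or sets an order. This largely stands. The literal rule is unlikely to be applied, so its extra second stage should not be presented as an expected cost. It remains true that a decision threshold is wrong as printed.

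On 36, section 9 gives the 95% detection figure shortly before the trigger, and the arithmetic fits. A reader might infer that a bilateral rate cannot explain 36, because section 8 needs only one SLN of type 1 or 2 for the ICG sensitivity analysis, so patients mapped on one side are not lost. That goes too far: it shows that a bilateral rate is a poor choice of allowance, not that 36 came from elsewhere. What survives is that the link is unstated.

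On enrolment, section 9's expected gain from ultrasectioning could offset the 15 extra patients: 34/(226 × 0.95) = 15.8% node-positivity would be enough. But section 11 already puts that gain inside its 15%, so the two sections still disagree. The effect is small, since both make the LN+ count decisive rather than 226 or 227.

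**Conclusion.** The point holds as an inconsistency that should be fixed. Among the readings of the success stop examined, with the other bounds as written, only 33 or more of 34 yields the stated type I error (0.049). The printed rule is conservative at 0.035 and loses 0.029 of power at 92.5% and 0.015 at 95%. A reader might infer that the misprint inflates false-positive risk or exposes patients to harm. It does neither: the error falls, and section 9 keeps full lymphadenectomy in place whatever the interim shows.

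The 34/36 mismatch matters more for error control, because the two natural ways of carrying the bounds over give 0.193 and 0.043. The plan does not prescribe the reading that gives 0.193. The finding is that nothing written excludes it.

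These figures assume independent binomial outcomes in LN+ patients, and the literal rule assumes the 33 are the first 33 in sequence. Correcting the bound does not rescue the power statement: power is 0.517 at 92.5% and reaches the stated 0.8 only at 95% (0.805).

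**What to change.** In section 11, replace the stage-1 rule with: *Stage 1 is the first 34 evaluable LN+ patients. Stop for futility if 30 or fewer are SLN+; continue to 62 if 31 or 32; stop and reject H0 if 33 or 34. Later LN+ patients do not enter the stage-1 decision but count toward the 62.*

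The sponsor should define evaluable from its own primary endpoint. Section 8 describes both an ICG set (at least one SLN type 1 or 2) and an overall concept that includes SLN macro, and section 11 does not choose between them.

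In the Overview and section 9, either replace 36 by the 34th evaluable LN+ patient, or keep 36 as the enrolment trigger and state that only the first 34 evaluable are tested against these bounds.

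Make sections 9 and 11 agree on whether 226/227 includes the detection allowance and on how the ultrasectioning gain is counted. Restate the power sentence separately.

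The cost is wording in three places, plus the sponsor's decision on the evaluable set. Correcting the bounds and the trigger needs no additional patients or data.

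### The stated power of 0.8 at a true sensitivity of 92.5% is wrong: the two-stage rule has about 52% power there and reaches 80% only at about 95%

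*Combined protocol and SAP*

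**What the plan says.** All the design inputs are in section 11 (Statistical Considerations) of the combined protocol and SAP.

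- Hypothesis: "The null hypothesis that the sensitivity is 85% will be tested against one-sided alternative".
- Stage 1 size: "In the first stage, 34 LN+ patients will be accrued".
- Futility: "If there are 30 or fewer responses in these 34 patients, the study will be stopped for futility".
- Early rejection: "If there are at least 33 responses in 33 patients, the study will be stopped and the null hypothesis rejected".
- Final test, after 28 more node-positive patients: "The null hypothesis will be rejected if 58 or more responses are observed in 62 patients".
- Operating characteristics: "This design yields a type I error rate of 0.05 and power of 0.8 when the true sensitivity is 92.5".

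The same paragraph explains the stage 1 stop with a different sensitivity. It begins "The study is terminated after stage one if it is unlikely that the sensitivity is" and, after a greater-or-equal sign, continues "95% or if sensitivity is significantly higher than 85" per cent. So 95% appears in the stopping rationale and 92.5% in the power statement. No other section gives a power figure.

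**The concern.** Two different sensitivities stand in one paragraph as the value the design is meant to detect, and 62 observations looks small for separating 92.5% from 85% with 80% power. Sensitivity is the main endpoint and this sentence is the only power justification in the document. It supports the 34 + 28 node-positive patients and, through them, the planned enrolment of about 413.

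If the sentence is wrong, readers are told that a technique with 92.5% sensitivity has a four-in-five chance of being shown better than 85% when the chance is much lower. A futility stop or a non-significant final result could then be taken as evidence against 92.5%, although the design could not reliably detect that value.

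**Working it through.** **Inputs (all from section 11).** Null p0 = 0.85, one-sided. Stage 1: n1 = 34, with futility at 30 or fewer. Stage 2: n2 = 28, with final rejection at 58 or more of 62. The early-rejection bound is printed as 33 of 33, which cannot be right for a 34-patient stage. I read it first as 33 or more of 34 and then try the alternatives.

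**Formula.** With X1 ~ Bin(34, p) and X2 ~ Bin(28, p), only X1 = 31 or 32 leads to stage 2, so

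P(reject) = P(X1 ≥ 33) + P(X1 = 31)·P(X2 ≥ 27) + P(X1 = 32)·P(X2 ≥ 26).

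**Type I error, p = 0.85.** 0.0279 + 0.1310 × 0.0627 + 0.0696 × 0.1871 = 0.0279 + 0.0082 + 0.0130 = 0.0491. This agrees with the stated 0.05.

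**Power at the stated alternative, p = 0.925.** 0.2652 + 0.2252 × 0.3686 + 0.2604 × 0.6487 = 0.2652 + 0.0830 + 0.1689 = 0.517. The plan says 0.8.

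**Power at p = 0.95.** 0.4877 + 0.1525 × 0.5883 + 0.2717 × 0.8373 = 0.4877 + 0.0897 + 0.2275 = 0.805. This agrees with the stated 0.8.

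| True sensitivity | P(reject) | P(futility stop at stage 1) |
|---|---|---|
| 85% | 0.049 | 0.772 |
| 92.5% | 0.517 | 0.249 |
| 93% | 0.575 | 0.212 |
| 94% | 0.694 | 0.145 |
| 95% | 0.805 | 0.088 |

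Solving for 80% power gives a true sensitivity of 94.95%.

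**Other readings of the rule.**

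| Reading | Type I error | Power at 92.5% | Power at 95% |
|---|---|---|---|
| Early rejection at ≥33 of 34 | 0.049 | 0.517 | 0.805 |
| Early rejection only at 34 of 34 | 0.034 | 0.487 | 0.790 |
| No early rejection | 0.033 | 0.483 | 0.788 |
| Single stage, ≥58 of 62 | 0.034 | 0.499 | 0.802 |
| Literal 33 of 33, then 29 more (N = 62) | 0.027 | 0.412 | 0.708 |
| Literal 33 of 33, then 28 more (N = 61) | 0.015 | 0.307 | 0.610 |
| Interim at 36, then 26 more, early rejection at 36 | 0.036 | 0.502 | 0.804 |
| Interim at 36, then 28 more (N = 64), early rejection at 35, final bound still 58 | 0.139 | 0.797 | 0.959 |

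The interim count of 36 comes from the overview study plan and section 9. Only the last row approaches 0.8 at 92.5%, and its type I error is 0.139.

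**An upper limit that does not depend on the stopping bounds.** By the Neyman–Pearson lemma, the most powerful level-0.05 test on 62 observations rejects at 58 or more and randomises at 57. Its randomisation probability is (0.05 − 0.0345)/0.0466 = 0.333. Its power at 92.5% is 0.4992 + 0.333 × 0.1804 = 0.559. Early stopping cannot exceed this, so no set of bounds with at most 62 node-positive patients gives 80% power at 92.5% with type I error 0.05.

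**Scale.** The smallest exact single-stage test of 85% against 92.5% with 80% power has 118 node-positive patients (reject at 107 or more). Against 95% it has 59 (reject at 55 or more), close to the planned 62. Exact power does not rise smoothly with n, so 118 is indicative only.

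**The case against.** The arithmetic is hard to contest, but four points can be made against how far it goes.

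- **The 52% is not the literal rule.** The printed early-rejection bound is 33 of 33, and 52% requires reading it as 33 of 34. The agreement of the type I error with 0.05 also depends on that reading, because the other 34-patient readings give 0.033 to 0.034. This stands and must be disclosed. It does not help the stated power: with the stated bounds and a 34-patient first stage, 33 of 34 is the most favourable reading, and the literal ones give 0.31 to 0.41.
- **The intended alternative is not proven.** The 95% in the stopping rationale and the fit of the numbers make a slip likely, but the plan never names 95% as the design alternative. This also stands, and the sponsor has to confirm it.
- **The practical harm may be small.** If 95% was intended, the sample size and decision rule do not change and one descriptive sentence is wrong. All patients have a full lymphadenectomy under the national protocol, and section 9 says this holds even in the event of futility. That limits the consequence for patients. It does not make the only power claim for the main endpoint correct.
- **Misreading a negative result is a prediction about readers.** That is fair, and section 1 frames the objective as estimating sensitivity and negative predictive value. The futility and rejection rules are nevertheless binding decisions whose stated chances are wrong.

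**Conclusion.** The concern holds. The stated power of 0.8 at 92.5% is about 28 points too high: the exact value is 0.517, and a trial at that true sensitivity stops for futility at stage 1 with probability 0.249. The rule does match the stated error rates, with type I error 0.049 and power 0.805, when the alternative is 95%.

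This rests on exact binomial calculation with one result per node-positive patient, the section 11 sizes and bounds, and early rejection at 33 or more of 34. If early rejection needs all 34, or is not used, power is 0.48 to 0.49 at 92.5% and 0.79 at 95%, so the conclusion is unchanged. Type I error is controlled on every reading that keeps the section 11 sizes and bounds. The defect is in the power statement. It should be corrected because it is the sole justification for the sample size on the main endpoint.

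**What to change.** 1. In the power sentence of section 11, replace 92.5 with 95%, subject to the sponsor confirming that 95% was the design alternative.
2. Report the operating characteristics beside it: type I error 0.049; power 0.80 at 95%, 0.69 at 94% and 0.52 at 92.5%; probability of a stage 1 futility stop 0.25 at 92.5%. Add that failure to reject does not exclude a sensitivity of 92.5%.
3. Before those figures are printed, correct the 33-of-33 bound and reconcile the interim count, which is 34 in section 11 and 36 in the overview and section 9. If the settled rule differs from 33 or more of 34, recompute the figures.
4. If 92.5% was in fact the intended alternative, correcting the sentence is not enough. Sizes and bounds must be recalculated, to roughly 118 node-positive patients on a single-stage basis.

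Steps 1 to 3 cost a short protocol and SAP amendment and a less favourable stated power at 92.5%, with no extra patients. Step 4 would nearly double the node-positive requirement (118/62 = 1.9).

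### The stage 1 total of 226 is 34/0.15 and contains no allowance for 95% bilateral detection, although section 11 says it does; and the interim trigger of 36 node-positive patients is not linked to the 34 for which the stage 1 rule is written

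*Combined protocol and SAP*

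**What the plan says.** **Enrolment in section 11 (Statistical considerations).** The stage 1 total is introduced as follows: "For the first stage we estimated a total of 226 patients to be included taking into consideration a 95% bilateral SLN detection rate". The same sentence gives 15% node positivity and says that this 15% already includes the increase expected from ultrasectioning and immunohistochemistry. Stage 2 adds 187 patients. Section 11 also says that the running count of node-positive patients decides how many are included in each stage.

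**Enrolment in section 9 (Duration of study).** At 15% prevalence, "227 patients will be needed to obtain 34 lymph node positive observations". Next comes the allowance: "Given a 95% bilateral detection rate of SLN's approximately 15 patients more will need to be included". Section 9 then names an opposing effect, a rise in node positivity from ultrasectioning and immunohistochemistry, without putting a number on it. The calendar goes back to the smaller figure: "a total of 45 months will be required to reach 226 cervical cancer patients". It assumes that "the accrual rate is 2,5 cervical cancer patients per month per center", and the same section describes "a planned later inclusion of the second investigating center".

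**Interim count.** Section 9 says "an interim analysis will start after 36 node positive patients regardless of the total number of patients included", and the overview study plan gives the same 36. Section 11 says "In the first stage, 34 LN+ patients will be accrued" and sets the futility limit (30 or fewer responses) for those 34. If the study continues, 28 more make 62.

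**Who counts for sensitivity.** Section 8 requires at least one SLN of type 1 or 2. Section 6 excludes patients converted to open surgery before SLN removal. Neither section requires bilateral detection.

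**The concern.** A planned enrolment should follow from the inputs named for it. Here one input, the 95% detection rate, is said to be in the figure and is not. Section 9 treats the same quotient as the number before that allowance. A reader therefore cannot tell whether the plan allows for patients lost to the sensitivity analysis, or at what rate.

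The interim count raises a related question. If 36 node-positive patients were meant to yield 34 evaluable ones, the plan should say so. If nearly all 36 are evaluable under sections 6 and 8, the analysis would begin with more patients than the stage 1 rule covers. It would then have to be decided, with data in hand, which 34 to use or how to adapt the limits.

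**Working it through.** **Inputs.** Stage 1: 34 node-positive patients; stage 2: 28 more; total 62 (section 11). Node positivity 15% (sections 9 and 11). Bilateral detection 95% (sections 9 and 11). Interim trigger 36 (overview, section 9). Accrual 2.5 per month per centre (section 9).

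**1. Reproduce the printed totals.** Patients = node-positive patients / 0.15.
- Stage 1: 34/0.15 = 226.7. Rounded down this is 226, rounded up 227.
- Stage 2: 28/0.15 = 186.7, printed as 187.
- Both stages: 62/0.15 = 413.3, printed as 413.

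All the printed totals are reproduced without a detection factor. Section 11 claims the allowance for stage 1 only.

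**2. Apply both inputs that section 11 names.** 34/(0.15 x 0.95) = 238.6, so 239. This is 13 more than 226. At 226 patients the expected node-positive count is 226 x 0.15 = 33.9, of which 33.9 x 0.95 = 32.2 would be left at 95%.

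**3. Could ultrasectioning make up the difference?** For 226 to include the 95%, node positivity would have to be 34/(226 x 0.95) = 15.8%. Section 11 states 15% with the gain already included, so as written the gain cannot be used a second time.

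**4. Totals by loss rate.** The documents give no loss rate for the set defined in sections 6 and 8, so the range below is an assumption. Formula: N = (node-positive patients / 0.15) / (1 - loss), rounded up.

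| Assumed loss | Stage 1 | Both stages |
|---|---|---|
| 0% | 227 | 414 |
| 1% | 229 | 418 |
| 2% | 232 | 422 |
| 3% | 234 | 427 |
| 5% | 239 | 436 |

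**5. Calendar.** 226/45 = 5.02 per month, which is two centres at 2.5 from the first patient. At 5 per month, 226 takes 45.2 months and 239 takes 47.8. With one centre throughout, 226 would take 226/2.5 = 90.4 months.

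**6. The trigger of 36.**
- 34/0.95 = 35.8, which rounds to 36: a plausible origin, stated nowhere.
- 36/0.15 = 240 patients, in line with 239 and not with 226.
- Evaluable patients at the trigger: 36 at 0% loss; 36 x 0.95 = 34.2 at 5% loss. Exactly 34 needs a loss of 1 - 34/36 = 5.6%.

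**7. Why the analysed number matters.** Suppose, for illustration only, that the futility limit of 30 or fewer were applied unchanged. At a true sensitivity of 85%, the binomial probability of stopping is 0.77 with 34 patients and 0.46 with 36. The documents do not say that this would be done.

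**The case against.** The strongest reply is that little depends on 226. The node-positive count decides accrual, and section 9 starts the interim analysis whatever the total. Sections 9 and 11 both foresee that the accrual time may be revised as centres join. This stands, and it limits the point to planning figures and the interim count.

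A second reply is that section 11 compresses section 9, where about 15 extra patients are set against a gain from ultrasectioning and the plan settles on 226. The gap to be filled is only 15% against 15.8%. This may be how the figure arose, but section 11 puts the gain inside its 15%, so the sentence is wrong as it stands.

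Third, 226 and 227 are one quotient rounded two ways, both sections end on 226, and neither 239 nor the sum 227 + 15 = 242 is printed. This also stands. A reader might infer that the documents print several rival enrolment targets; they do not. Nor is the approximate 15 worth correcting against the 12 given by 227/0.95 = 238.9, since the text presents it as approximate.

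Fourth, a reader might infer that 34 and 36 contradict each other, or that the plan never says what they count. The documents support neither. They call 34, 36 and 62 node-positive patients, and 36 may simply be when the analysis starts and 34 the number it needs. What is missing is the link between the two, and between both and the set defined in sections 6 and 8.

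**Conclusion.** The point holds in two limited parts.

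First, the stage 1 total does not have the basis that section 11 claims for it. It is 34/0.15; the two stated inputs together give 239, a difference of 13 patients and about 3 months at 5 per month. A reader might conclude that 226 is too small or that the trial loses power. The documents do not support that: type I error and power do not depend on 226, and at zero loss 226 is right within rounding. Whether it is too small depends on a loss rate that the plan does not give for the set it analyses. The 3 months are also small beside the uncertainty about when the second centre joins.

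Second, the trigger of 36 and the rule for 34 are not linked. The likely link, 34/0.95, uses bilateral detection, which is not how sections 6 and 8 define the sensitivity set. Between 34 and 36 evaluable patients could be on hand when loss is between 5.6% and zero, and section 11 has no stage 1 rule for more than 34. This part matters more, because it bears on what is analysed at the interim.

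The arithmetic is certain. The 0% to 5% loss range is an assumption.

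**What to change.** Text changes only.

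1. **Enrolment.** Either delete the statement that 226 includes the 95% allowance and give 227 for stage 1 (414 in total) as the figures at zero loss; or state an assumed loss rate for the set defined in sections 6 and 8 (no conversion before SLN removal, at least one SLN type 1 or 2) and restate the totals. At 5% loss, for example, these are 239 for stage 1 and 436 in total, with about 48 months to the end of stage 1 at 5 per month.
2. **Consistency.** Use the same stage 1 figure in sections 9 and 11, bring the allowance of about 15 in section 9 into line with the option chosen, and base the calendar on that figure.
3. **Interim.** State that the stage 1 and final rules apply to 34 and 62 evaluable node-positive patients. Start the interim analysis when the 34th evaluable node-positive patient is reached, and give 36 only as the expected node-positive count at about 5% loss. Make the same change in the overview.

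The cost is small. Accrual still runs on node-positive counts, now specified as evaluable. The stated plan becomes slightly larger and longer if a loss rate is assumed.
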